5.1.4 Complementary output

Additional analyses of the immune responses elicited by CYD dengue vaccine booster by age group (9-17 years and 18-45 years) and by pre-booster dengue status will be provided in Appendix 15 of the CSR.

Immunogenicity analyses:

- GMTRs (post-booster / PD3) against each of the 4 parental dengue serotypes in Group 1 only
- GMTs against each of the 4 parental dengue serotypes
- GMTRs (post-booster / pre-booster) against each of the 4 parental dengue serotypes
- Number and percentages of subjects ≥ 10 (1/dil) against each dengue serotype with the parental dengue virus strains at each available time point
- Seroconversion rates based on pre- and post-booster titers

Safety analyses:

- Overview and summary tables of AEs after booster dose
- SAEs including serious AESIs by SOC and PT
- Non-serious AESIs by SOC and PT

5.2 Analysis Sets

Six analysis sets will be used: PPAS, FAS, SafAS, the enrolled subjects set, the randomized subjects set, and the AIT set.

5.2.1 Per-Protocol Analysis Set

The PPAS is a subset of the FAS. It will include all subjects who had no protocol deviations from the present study. Subjects will be excluded from the PPAS for the following reasons:

- Subject did not meet all protocol-specified inclusion/exclusion criteria
- Subject did not receive study injection
- Subject received a vaccine other than the one that he / she was randomized to receive
- Preparation and / or administration of vaccine was not done as per-protocol
- Subject did not provide the post-dose serology sample at Visit 4 (D28) in the proper time window
- Subject received a protocol-restricted medications (see protocol Section 6.7)
- Subject's post-injection serology sample did not produce a valid test result (i.e. a result different from "NR" or missing, for at least one dengue serotype)

Subjects will remain in this population as long as they do not meet one of the above criteria, except for blood sampling timing and validity of the serology test result.

5.2.2 Full Analysis Set

The FAS is defined as the subjects who received either CYD dengue vaccine or placebo and had blood sample drawn and valid post-injection serology results (i.e. a result different from "NR" or missing, for at least one dengue serotype). Subjects will be analyzed by the vaccine group to which they were randomized.

5.2.3 Safety Analysis Set

The SafAS is defined as those subjects who have received either CYD dengue vaccine or placebo^a. All subjects will have their safety analyzed according to the vaccine they actually received.

Safety data recorded for a vaccine received out of the protocol design will be excluded from the analysis (and listed separately).

5.2.4 Other Analysis Sets

Enrolled subjects set

Enrolled subjects are subjects for whom a CRF has been created.

Randomized subjects set

Randomized subjects are subjects who were randomly assigned to Group 1 or Group 2.

AIT subset

The AIT subset is defined as those subjects who belong to the Randomized subjects set but had additional blood samples drawn for the assessment of CMI, additional neutralizing Ab titers (for exploration of the Ab response's kinetics), and Ab specificity and affinity maturation in the present trial. The AIT subset will include the first 60 randomized subjects from two specific sites (30 subjects per site): 45 subjects from Group 1 and 15 subjects in Group 2.

5.2.5 Populations Used in Analyses

The PPAS will be used for the analysis for the primary objective. The FAS will be used for the superiority hypotheses testing for first secondary objective. All the immunogenicity analyses for immune response elicited by booster dose will be performed on the PPAS, and will be confirmed on the FAS. The immunogenicity Ab persistence analysis will be performed on the FAS. Subjects will be analyzed according to the vaccine group they were randomized to.

The SafAS will be used for the description of clinical safety. Subjects will be analyzed according to the product they actually received.

Enrolled subjects and randomized subjects will be used for various standard population tables including duration of the study, disposition of participants and deviations. Demographic and baseline characteristics will be presented on the PPAS and FAS.

The AIT subset will be used to describe additional neutralizing Ab levels in this subset, Ab specificity and affinity maturation, and CMI responses. Subjects will be analyzed by the vaccine group to which they were randomized.

^a for which safety data are scheduled to be collected

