5.2.4 Inclusion Criteria

An individual must fulfill *all* of the following criteria in order to be eligible for trial enrollment:

- 1) Has been identified as a potential subject by the Sponsor, and is included in the list provided to the Investigator (i.e., aged 9 to 45 years on the day of first injection of CYD dengue vaccine in CYD28, has received 3 doses of CYD dengue vaccine in the CYD28 trial, and has a PD3 serum sample available [at least 300 µL of serum]).

- 2) Presently in good health, based on medical history and physical examination.
- 3) Informed consent form (ICF) has been signed and dated by the subject (based on local regulations), and ICF has been signed and dated by the parent(s) or another legally acceptable representative (and by an independent witness if required by local regulations)
- 4) Subject and parent(s)/legally acceptable representative(s) able to attend all scheduled visits and to comply with all trial procedures

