‡ In female subjects of childbearing potential (i.e. women and girls who have reached menarche and who had not surgical sterilization, or hysterectomy).
§ Blood samples planned during vaccination visit will be taken before vaccination
** Solicited injection site reactions will be collected for 7 days after injection. Solicited systemic reactions will be collected for 14 days after injection. Unsolicited AEs will be collected for 28 days after injection.
†† Telephone call to contact the subjects and ask them about SAEs that may have occurred
‡‡ Serious AESIs will be reported after each injection in defined time windows as follows: serious hypersensitivity/allergic reactions occurring within 7 days, serious viscerotropic disease occurring within 30 days, serious neurotropic disease occurring within 30 days; hospitalized suspected dengue disease will be reported during the entire study. Non-serious AESIs (i.e. hypersensitivity / allergic reactions) will be reported within 7 days after each injection.
§§ In the AIT subset of 60 subjects (45 subjects in Group 1 and 15 subjects in Group 2).

4 Endpoints and Assessment Methods

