4.2 Secondary Endpoints and Assessment Methods

4.2.1 Immunogenicity

4.2.1.1 Immunogenicity Endpoints

The secondary endpoints for the evaluation of immunogenicity are:

- 1) Neutralizing Ab levels against each of the four parental dengue virus strains of CYD dengue vaccine as determined by PRNT measured 28 days after the third CYD dengue vaccine injection received in CYD28 trial and 28 days post-booster injection (subjects from Group 1 only).
- 2) Neutralizing Ab levels against each of the four parental dengue virus strains of the CYD dengue vaccine as determined by PRNT immediately prior and 28 days post-booster or placebo injection.

- 3) Individual post-booster/pre-booster GMTRs for each of the four parental dengue virus strains of the CYD dengue vaccine as determined by PRNT immediately prior and 28 days post-booster or placebo injection.
- 4) Seroconversion rates 28 days after the injection for each of the four parental dengue virus strain of CYD dengue vaccine; percentages of subjects with either a pre-booster titer < 10 (1/dilution [dil]) and a post-booster dose titer ≥ 40 (1/dil), or a pre-booster titer ≥ 10 (1/dil) and a ≥ 4 -fold increase in post-booster dose titer as determined by PRNT immediately prior and 28 days post-injection.
- 5) Neutralizing Ab levels against each of the four parental dengue virus strains as determined by PRNT at 28 days after the third CYD dengue vaccine injection received in CYD28 trial and immediately prior to booster or placebo injection in all study subjects.
- 6) Neutralizing Ab levels against each of the four parental dengue virus strains as determined by PRNT at 6 months, 1 year and 2 years post booster or placebo injection in all study subjects.

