5.1.2.2.2 Statistical Methods

5.1.2.2.2.1 Immunogenicity

Response elicited by booster dose

The time point to be used for the descriptive comparisons to describe the immune response elicited by CYD dengue vaccine booster (Group 1) as compared to placebo among subjects who received 3 doses of CYD dengue vaccine in CYD28 trial will be immediately prior to and 28 days post-Booster administration. Immunogenicity will be assessed descriptively using the following parameters:

- GMTs against each serotype with the parental dengue virus strains at each available time point
- Geometric mean of the individual titers ratio (GMTRs) against each serotype with the parental dengue virus strains
- Number and percentage of subjects ≥ 10 (1/dil) against each dengue serotype with the parental dengue virus strains at each available time point
- Number and percentage of subjects ≥ 10 (1/dil) against at least 1, 2, 3, or 4 dengue serotypes with the parental dengue virus strains at each available time point
- Number and percentage of subjects \geq various titer thresholds (1/dil) for at least 1, 2, 3, or 4 serotypes with parental dengue virus strains at each available time point
- Distribution of titers against each of the 4 serotypes with parental dengue virus strains at each available time point and corresponding RCDC
- Seroconversion rates 28 days after the injection for each of the four parental dengue virus strain of CYD dengue vaccine.

Two sample t-test on the log₁₀ transformed titers will be used for 95% CI for the ratio of GMTs (difference between GMTs on log scale).

Ab persistence

- At baseline: the time points to be used for the descriptive comparisons to describe neutralizing Ab persistence will be D0 (immediately prior to booster or placebo injection) and 28 days after the third CYD dengue vaccine dose in CYD28 subjects.
- At 6 months, 1 year and 2 years: the time points to be used to describe neutralizing Ab persistence will be 6 months, 1 year and 2 years after the booster or placebo injection.

Immunogenicity will be assessed descriptively using the same statistical methods and parameters as above.

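### The PD3-to-Day 0 persistence comparison is run on the FAS, so subjects with no valid post-injection titer drop out of an endpoint that uses only pre-injection samples

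*SAP*

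**What the plan says.** - **Population.** SAP 5.2.5: "The immunogenicity Ab persistence analysis will be performed on the FAS". No separate set is named for the part of persistence that lies before the injection.
- **What counts as persistence.** SAP 5.1.2.2.2 includes a baseline part. The time points to "describe neutralizing Ab persistence will be D0 (immediately prior to booster or placebo injection) and 28 days after the third CYD dengue vaccine dose" are both earlier than the CYD63 injection.
- **FAS entry.** SAP 5.2.2 (and Protocol 12.2.2) takes subjects who were injected and "had blood sample drawn and valid post-injection serology results", with a usable result for one serotype being enough. No visit is named.
- **The endpoint.** Secondary endpoint 5 in SAP 4.2.1.1 concerns titers 28 days after dose 3 "received in CYD28 trial and immediately prior to booster or placebo injection in all study subjects".
- **The samples.** Protocol 5.2.4 makes it an inclusion condition that the subject "has a PD3 serum sample available". For Day 0, a footnote to SAP Table 3.1 reads: "Blood samples planned during vaccination visit will be taken before vaccination".
- **Missing titers.** SAP 5.3.1 does not impute them.

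**The concern.** Whether a subject contributes to endpoint 5 depends on a later event that the endpoint does not use. Someone who has a valid PD3 titer and a valid Day 0 titer, is injected, and then leaves before giving any usable post-injection serum has complete data for the question but is excluded from the table.

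Two things are at stake, both modest. Some usable pairs are lost from the description of persistence five years or more after dose 3, which Protocol 5.1.2 names as a purpose of the design. The analysed group is also conditioned on remaining in the trial after the injection. Protocol 5.2.10 lists serious and other adverse events among the reasons for leaving, so that condition need not be unrelated to health.

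**Working it through.** **Step 1: does the FAS rule reach this comparison?** Yes. SAP 5.1.2.2.2 puts PD3 versus Day 0 under antibody persistence, and SAP 5.2.5 assigns persistence to the FAS without exception. The available-pair rule for the primary analysis (SAP 5.1.1.2) is not extended to endpoint 5.

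**Step 2: who is lost?** The FAS names no visit and accepts one valid serotype.

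| Subject, injected, with valid PD3 and Day 0 titers | In the FAS? |
|---|---|
| Outside the AIT subset (260 − 60 = 200 planned), leaves before Day 28 | No |
| AIT subset (60 planned), leaves before any valid D7 or D14 titer | No |
| AIT subset, valid D7 or D14 titer, then leaves | Yes |
| Misses Day 28, valid titer at a later visit | Yes |
| Non-reportable for some serotypes, valid for at least one | Yes |
| No valid result for any serotype at any post-injection visit | No |

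SAP 5.4 plans a first analysis on data up to Day 28. If the FAS is derived again at each lock, which the SAP does not state, the subject in the fourth row would be absent at first and enter later.

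**Step 3: the plan's own figure.** SAP 5.5 assumes 10% in each group without valid immunogenicity results.

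- Group 1: 195 × 0.90 = 175.5, rounded up to 176 (matches).
- Group 2: 65 × 0.90 = 58.5, rounded up to 59 (matches).
- Together: 176 + 59 = 235 of 260.

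**Step 4: the ceiling.** SAP 5.1.1 defines evaluable subjects as those in the PPAS with valid titers. The PPAS is a subset of the FAS, so under the plan's own allowance FAS loss cannot exceed PPAS loss.

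- Subjects: at most 260 − 235 = 25.
- CI width on the log scale, FAS relative to all pairs: √(260/235) = 1.052, about 5% wider.

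**Step 5: a range.** The documents give no rate of having no valid post-injection result. With an assumed fraction d, lost subjects = 260 × d and width ratio = √(1/(1 − d)).

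| Assumed d | Subjects lost | CI width ratio |
|---|---|---|
| 1% | 2.6, about 3 | 1.005 |
| 2% | 5.2, about 5 | 1.010 |
| 5% | 13 | 1.026 |
| 10% | 26 | 1.054 |

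The last row differs from the ceiling of 25 only because the plan rounds each group up.

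**Step 6: possible shift in the estimate.** If the lost subjects differ from the rest by Δ in mean log10(D0/PD3), leaving them out changes the geometric mean ratio by a factor of 10^(d × Δ). For assumed Δ of 0.1 to 0.5:

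- d = 1%: 10^0.001 = 1.002 to 10^0.005 = 1.012.
- d = 10%: 10^0.01 = 1.02 to 10^0.05 = 1.12.

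Nothing in the documents supplies a value of Δ; these figures only show scale.

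**The case against.** **One set for the whole series.** The best defence is that a single FAS for PD3, Day 0, 6 months, 1 year and 2 years keeps the persistence tables on the same people. This does not hold up. Missing titers are not imputed and one valid result at any visit is enough to enter, so the number analysed already differs by time point and serotype.

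**The FAS is already the wider choice.** Protocol 12.2.4 puts immunogenicity analyses on the PPAS with the FAS as confirmation, and has no separate rule for persistence. SAP 5.2.5 is less restrictive than that. True, but the FAS still carries a post-injection condition.

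**Readings that go too far.** Several stronger inferences are tempting, and the documents do not support them.

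- *Anyone who withdraws before Day 28, or has a non-reportable sample, is removed.* Only a subject with no valid result for any serotype at any post-injection visit is removed.
- *The plan expects to lose 10% here.* The allowance is linked to PPAS evaluability. It has to cover out-of-window Day 28 samples and restricted medication, and such subjects can stay in the FAS. It can also cover invalid PD3 titers, which no change of set would recover.
- *Both samples always exist.* Protocol 5.1.4 lets a subject be injected when no baseline blood can be obtained, and Protocol 5.2.4 requires stored PD3 serum, not a valid titer.
- *The endpoint wording flatly contradicts the FAS.* The phrase "immediately prior to booster or placebo injection in all study subjects" can be read as both arms, in contrast to the Group 1 restriction in endpoint 1. Endpoint 6 also refers to all study subjects, and the FAS is reasonable there. The case rests on the timing of the samples, not on that phrase.
- *The persistence estimate is biased.* No passage links the D0/PD3 ratio to dropout after the injection.

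**Conclusion.** The point holds, and it is small. SAP 5.2.5, 5.1.2.2.2 and 5.2.2 together condition a wholly pre-injection comparison on a post-injection result, and no other rule in either document lifts that condition. Those affected are mainly subjects outside the AIT subset who leave before Day 28 and AIT subjects who leave before a valid D7 or D14 titer.

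On the plan's own allowance the loss is at most about 25 of 260 subjects, with a CI about 5% wider. A few subjects is more likely, though that is a judgement because the documents give no rate. The size also assumes that the excluded subjects have valid PD3 and Day 0 titers. The endpoint is secondary and descriptive. The primary non-inferiority test, the superiority test and the sample size are unaffected. This is an inexpensive improvement and does not undermine any conclusion of the trial.

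**What to change.** In SAP 5.2.5, state that endpoint 5 (PD3 and Day 0 GMTs, the D0/PD3 GMTR, and seropositivity) is analysed on all injected subjects with valid PD3 and Day 0 titers for the serotype concerned, whether or not a post-injection result exists. Keep the FAS for persistence at 6 months, 1 year and 2 years.

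The set should be injected rather than randomized subjects. In the Visit 1 steps of Protocol 5.1.4, randomization comes before both the baseline draw and the injection, so a randomized set could include people never injected, for whom a titer just before injection has no meaning.

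The cost is one sentence and one population flag. Protocol 9.1.1.2 already plans PRNT on the CYD28 post-dose-3 sample and the CYD63 Visit 1 sample for all subjects, so no new visit, sample or assay is needed.

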5.3 Handling of Missing Data and Outliers

5.3.1 Immunogenicity

The LLOQ management will be performed as described in [Section 4.4.1.1](#). Missing data will not be imputed. No test or search for outliers will be performed. The values assessed as aberrant by the Sanofi Pasteur Research Department in Marcy l’Etoile, France will be excluded from the statistical analysis.

5.3.2 Safety

No replacement will be done unless state otherwise. No search for outliers will be performed. In all subject listings, partial and missing data will be clearly indicated as missing.

5.3.2.1 Immediate

For unsolicited non-serious systemic AEs, a missing response to the “Immediate” field is assumed to have occurred after the 30-minute surveillance period and will not be imputed.

For SAEs, missing or partially missing elapsed time from last vaccination recorded if within 24 hours will remain missing and not be imputed. Such SAEs will not be considered as immediate.

5.3.2.2 Causality

Missing causality (relationship) for unsolicited non-serious AEs and SAEs will be considered at the time of analysis as related to vaccination.

5.3.2.3 Measurements

Missing measurement (for temperature or length) will not be replaced.

5.3.2.4 Intensity

For solicited reactions, missing intensities will be handled as described in [Section 4.4.2.1.1](#). For unsolicited non-serious AEs, missing intensities will remain missing and will not be imputed.

5.3.2.5 Start Date and Stop Date

Missing or partially missing start dates for unsolicited AEs will remain missing and not be imputed. If either the start or stop date is missing or partially missing, the time to onset will be considered to be missing. Nevertheless unsolicited AEs with missing time to onset will be included in analyses according to the visit collected.

Missing or partially missing stop dates for AEs (solicited reactions and unsolicited AEs) will remain missing and not be imputed.

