9.2.2.3.3 Unsolicited Non-serious Adverse Events From Day 0 to Day 28 After Vaccination

In addition to recording solicited reactions, subjects (or subjects' parent(s) / legally acceptable representative(s)) will be instructed to record any other medical events that may occur during the 28-day period after vaccination. Space will be provided in the DC for this purpose.

For each unsolicited non-serious AE, the following information is to be recorded:

- Start and stop dates^a
- Intensity of the event:
 - For measurable unsolicited non-serious AEs that are part of the list of solicited reactions, the size of the AE as well as the temperature for fever will be collected and analyzed based on the corresponding scale used for solicited reactions (see [Table 9.1](#) and [Table 9.2](#))
 - Other unsolicited non-serious AEs will be classified according to the following intensity scale:
 - Grade 1: No interference with activity
 - Grade 2: Some interference with activity
 - Grade 3: Significant; prevents daily activity
- Action taken for each AE, if any (e.g., medication)

The action taken by the subjects (or subjects' parent(s) / legally acceptable representative(s)) to treat any **unsolicited AEs** will be classified in the CRF using the following scale:

- 0: None
- 1: Medication (self-medication with an existing prescription or over-the-counter medication)
- 2: Health care provider contact (no new medication prescribed)

^a The stop date of all related AEs will be actively solicited. For other events, the investigator will provide the stop date when it becomes available. AEs for which no stop date was obtained during the course of the trial will be considered as ongoing at the end of the trial.

3: Health care provider contact and prescription of a new medication (health care provider instructed subject to take a new medication, either an over-the-counter medication or one requiring a written prescription)

- Whether the AE led to discontinuation
- Whether the AE was related to vaccination (for unsolicited systemic AEs). See [Section 9.2.2.3.6](#) for the assessment of causality.

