4.4.2 Safety

Terms used in the clinical safety tables to describe the safety events are specified below:

- AE: Adverse event; includes immediate, solicited, and unsolicited non-serious or serious adverse events.
- AR: Adverse reaction; Adverse reaction corresponds to an unsolicited related AE
- Immediate AE/AR: Unsolicited non-serious AE ticked "immediate (within 30 minutes from the vaccination)" by the investigator in the CRF or SAE with time of onset within 30 minutes
- Solicited reaction: Event pre-listed in the CRF, and which occurred during the solicited period (period is usually 0 to 7 days for injection site reactions and 0 to 14 days for systemic reactions post-vaccination)
- Unsolicited AE: AE recorded in the eCRF unsolicited form and SAE form, excluding solicited reactions. Therefore, this term includes immediate AEs/ARs.
- Unsolicited non-serious injection site events are always recorded without relationship and analyzed as ARs.
- SAE: Unsolicited AE considered serious by the investigator.
- Hospitalized suspected dengue case: Hospitalized suspected dengue disease is defined as an acute febrile illness with diagnosis of dengue requiring hospitalization (with bed attribution).
- Hospitalized virologically-confirmed dengue case: A virologically-confirmed dengue infection is defined as a suspected dengue which has positive sample for the dengue screen RT-PCR (i.e., \geq LLOQ) and/or the non-structural protein 1 (NS1) antigen (Ag) enzyme-linked immunosorbent assay (ELISA) is positive and/or the SimplexaTM dengue reverse transcription-polymerase chain reaction (RT-PCR) is positive. Dengue NS1 Ag ELISA positive is defined as sample ratio >1 by comparing the optical density reading of the sample to the optical density of the cutoff control serum. The SimplexaTM Dengue RT-PCR positive is defined as detected results for at least one dengue serotype.

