4.4.2.2.4 Time of Onset

Time of onset is derived from the start date of the unsolicited non-serious AE provided in the clinical database and the date of last vaccination:

- start date of the unsolicited non-serious AE - date of previous vaccination

The time of onset should be considered as missing only if one or both of the dates are missing or partially missing.

The unsolicited non-serious AEs will be analyzed “Within 28 days”, which corresponds to AEs with a time to onset between 0 and 28 days after vaccination or missing. An AE with missing time of onset will be considered to have occurred just after the vaccination indicated by the visit number, so will be included in these tables.

Note: Unsolicited non-serious AE that occurred before vaccination (negative time of onset) or with a time of onset higher than defined above will not be included in analysis, but will be listed separately.

Time of onset will be displayed by period as follows: D0-D3, D4-D7, D8-D14, \geq D15 and Missing.

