4.4.2.3.2 Time of Onset

Time of onset will be computed using the same methodology than for unsolicited non-serious AEs described in [Section 4.4.2.2.4](#).

SAEs will be analyzed throughout the study using the following periods:

- Within 28 days after injection
- During the 2-year follow-up period (i.e., from 28 days after injection until the last subject contact)
- During the study (i.e., all SAEs occurred during the study)

An SAE with missing time of onset will be considered to have occurred after the vaccination indicated by the visit number, so will be included in these tables. SAEs collected after Visits 1, 2 or 3 with missing time of onset will be included the table of SAEs analyzed “within 28 days”, and SAEs collected after Visits 4, 5 or 6 with missing time of onset will be included in the table of SAEs analyzed “during the 2-year follow-up period”.

Note: SAEs that occurred before vaccination (negative time to onset) will not be included in analysis, but will be listed separately.

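### SAP 5.3.2.5 makes time to onset depend on the stop date, contradicting SAP 4.4.2.2.4; if it is programmed, ongoing events with a known start date lose their onset

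*SAP*

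**What the plan says.** **The missing-data section.** SAP 5.3.2.5 states: "If either the start or stop date is missing or partially missing, the time to onset will be considered to be missing". It then says that "unsolicited AEs with missing time to onset will be included in analyses according to the visit collected". On stop dates it adds: "Missing or partially missing stop dates for AEs (solicited reactions and unsolicited AEs) will remain missing and not be imputed". SAEs fall under this, because SAP 4.4.2 defines the term as follows: "Unsolicited AE: AE recorded in the eCRF unsolicited form and SAE form, excluding solicited reactions".

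**The derivation section.** SAP 4.4.2.2.4 gives the onset formula for non-serious events as "start date of the unsolicited non-serious AE - date of previous vaccination" and continues: "The time of onset should be considered as missing only if one or both of the dates are missing or partially missing". SAP 4.4.2.3.2 uses the same method for SAEs.

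**What happens when onset is missing.** For non-serious AEs, SAP 4.4.2.2.4 keeps the event in the within-28-days tables. For SAEs, SAP 4.4.2.3.2 goes by visit: "SAEs collected after Visits 1, 2 or 3 with missing time of onset will be included the table of SAEs analyzed" within 28 days, while those collected after Visits 4, 5 or 6 go to the 2-year follow-up table.

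**Who has no stop date.** Protocol 9.2.2.3.3, in a footnote on unsolicited non-serious AEs, says: "AEs for which no stop date was obtained during the course of the trial will be considered as ongoing at the end of the trial".

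**The concern.** Onset is the interval from vaccination to the start of an event. When the event ended, or whether its end was recorded, has no bearing on it. A rule that deletes onset when the stop date is absent or partial throws away a known quantity, and it does so for a predictable group: events that have not resolved.

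Time to onset is a named element of the secondary safety endpoints for unsolicited AEs and for non-serious AESIs (SAP 4.2.2.1, items 4 and 6). It also decides whether a non-serious event is analysed or only listed, and which period table an SAE enters. Two programmers following different sections of the same SAP could therefore produce different safety tables from the same data.

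**Working it through.** The plan gives no figure to reproduce here, so the check sets the rules side by side and applies each to example dates.

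**Step 1: which dates each derived variable uses.**
- Onset (SAP 4.4.2.2.4; for SAEs via 4.4.2.3.2) = start date − vaccination date. No stop date.
- Duration (SAP 4.4.2.2.5; for SAEs via 4.4.2.3.3) = stop date − start date + 1. Missing if either is incomplete.
- Solicited reactions take their onset from daily intensities (SAP 4.4.2.1.4), so the problem is confined to unsolicited AEs and SAEs.

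**Step 2: whether the two rules can both hold.** The derivation section restricts missing onset to incompleteness of the two dates in its own formula. SAP 5.3.2.5 adds a third date. An event with complete start and vaccination dates but no stop date has a known onset under the first rule and a missing one under the second. They cannot be reconciled. The pairing of start and stop date in 5.3.2.5 is the pairing that duration needs, so the sentence may have been meant for duration; that is an inference.

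**Step 3: example events.** The dates are assumed; vaccination is Day 0 and the stop date is missing. Protocol 5.1.4 allows Visit 4 on Days 28 to 35 (28 + 7).

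| Event | Under SAP 4.4.2.2.4 / 4.4.2.3.2 | If SAP 5.3.2.5 is programmed |
|---|---|---|
| Non-serious AE, starts Day 5 | Onset 5; within 28 days, category D4–D7 | Within 28 days, category Missing |
| Non-serious AE, starts Day 33, recorded at Visit 4 on Day 35 | Onset 33; listed only | Counted within 28 days |
| Non-serious AE, start date before vaccination | Negative onset; listed only | Counted within 28 days |
| SAE, starts Day 20, collected after Visit 4 | Within 28 days | 2-year follow-up table |
| SAE, starts Day 33, collected before a Visit 4 on Day 35 | 2-year follow-up table | Within 28 days |

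**Step 4: what does not change.** A non-serious AE starting on Days 0 to 28 is counted under either rule; only its onset category differs. An SAE that moves between the two period tables still appears in the whole-study SAE table.

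**The case against.** The strongest reply is that the derivation section is explicit, gives the formula and says when onset may be missing. A programmer would probably follow it and treat the clause in 5.3.2.5 as stray. That is fair, and it makes every consequence above conditional. It does not remove the contradiction, because 5.3.2.5 is the section a programmer would consult for incomplete dates.

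The routes to misplacement are also narrow:
- SAEs must be reported within 24 hours (Protocol 10.1), so one starting by Day 28 would normally be collected before Visit 4 and stay in the right table. The error needs a late report as well as a missing stop date.
- The diary card covers 28 days (Protocol 9.2.2.3.3), so events after Day 28 would come up mainly at the Visit 4 interview.
- Pre-existing conditions are not AEs unless they worsen (Protocol 9.2.2.1), so few events should have a negative onset.

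A reader might infer more than the documents support:
- *That the 28-day window is inflated by about 24%.* Days 29 to 35 add 7 days to a 29-day window, and 7/29 = 24%. This is calendar time open only to events that start in those days, before a late Visit 4, and have no stop date. No safety percentage is shown to change by that amount.
- *That unrelated events are hit selectively, SAEs included.* The footnote on actively seeking stop dates for related events belongs to the non-serious AE section. SAEs have their own follow-up reporting (Protocol 9.2.2.3.4 and 10.2).
- *That SAEs collected at Visit 4 itself move to the follow-up table.* SAP 4.4.2.3.2 speaks of collection after Visits 4, 5 or 6.
- *That the AESI windows fail in the same way.* SAP 4.4.2.4.7 lists 7-day and 30-day windows without naming the variable that applies them, so this is possible but not stated.
- *That the Day 28 analysis suffers most.* Events unresolved at that lock would lack a stop date, but the documents give no count for any analysis.

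**Conclusion.** The contradiction is real, and 5.3.2.5 is wrong as written: it makes onset depend on a date that the onset formula does not use. If it governs, known onsets are lost for ongoing events and for those with a partial stop date. Non-serious AEs starting on Days 0 to 28 only change onset category. Those with a known onset outside that period are wrongly counted, and some SAEs change period table.

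The size cannot be stated. The documents do not give the share of events without a stop date. If that share were assumed to be 5%, 10% or 20%, the same share of unsolicited AEs with a known start date would lose its onset; this restates the assumption and does not estimate an effect on any reported rate. All the affected analyses are descriptive, and neither the non-inferiority nor the superiority test is touched. The conclusion rests on the text alone; the consequences rest on the further assumption that 5.3.2.5, not 4.4.2.2.4, is programmed.

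**What to change.** In SAP 5.3.2.5, replace the sentence on time to onset with one saying that it is missing only if the start date or the vaccination date is missing or partially missing. Keep the stop-date condition for duration alone, with a reference to 4.4.2.2.5. The visit-based allocation then applies only to events whose onset is truly unknown.

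The cost is one sentence in the SAP and a check that the onset program follows 4.4.2.2.4. No additional data are needed.
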